To address the gaps in cervical cancer screening, the ELEVATE project is developing a screening strategy to make cervical screening more accessible to hard-to-reach women. This strategy will include the introduction of a new on-site HPV self-sampling screening tool and a portable testing device, able to detect the presence of HPV and cancer biomarker proteins. This portable, low-cost, on-site HPV testing tool will allow to streamline follow-up care for women at risk of developing cervical cancer.

2. Background

Even though preventive approaches and strategies are different in European and Latin American contexts, coverage levels are not sufficient in all countries. In Ecuador, coverage at national level ranges between 9 to 20% (9). In Brazil, the coverage rate for the cervical cancer-screening program (opportunistic) is estimated to be below 70% (10). In Portugal and Belgium, screening coverages reaches 70.7% and 55%, respectively (11-14). This means that in all countries a significant part of the eligible female population is not screened regularly for cervical cancer (15,16). Those women, called "hard-to-reach women", are defined as women who are eligible for cervical cancer screening and who, for specific reasons to be further clarified in this study, do not participate in screening and consequently are at higher risk for cervical cancer. They are often from minority groups or living in isolated areas and face multiple barriers in accessing preventive care.

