3.2. Specific objectives

Objective 1: Assess and compare **attendance rates** following invitation to participate to the study

Hypothesis 1.1: Attendance will be higher when women are offered self-sampling compared to when women are only offered an educational session.

Objective 2: Evaluate the current **knowledge, willingness and uptake** of cervical cancer screening among participants of the acceptability study (arm 2 & 3); assess knowledge improvement and willingness to get screened 3 months after the intervention

Hypothesis 2.1: Knowledge and willingness to get screened will be poor and uptake of cervical cancer screening among the participants will be lower than the national average (but similar to results found in arm 1)

Hypothesis 2.2: After the information sessions, women will be able to link cervical cancer with HPV and will understand the benefit of screening; willingness to be screened will have increased

Objective 3: Assess **attitudes towards and users' experiences** of the HPV self-sampling test among hard-to-reach women (i.e. participants in arm 3)

Hypothesis 3.1: Attitudes towards on-site HPV self-sampling will be overall positive

Hypothesis 3.2: Women who use the self-sampling tool will have positive users' experiences related to the self-sampling device.

Objective 4: Compare the uptake of the on-site HPV testing (arm3) with the current national screening services (arm1) and with off-site referrals (arm2)

Hypothesis 4.1: Uptake of on-site HPV self-sampling will result in an increase in screening coverage compared to standard practices. (arm 3 vs arm 1)

Hypothesis 4.2: On-site HPV self-sampling will have higher uptake than referrals to off-site screening. (arm 3 vs arm 2)

Hypothesis 4.3: Referral to off-site screening following participation in an educational session on cervical cancer will result in higher screening coverage compared to current practices. (arm 2 vs arm 1)

Hypothesis 4.4: Uptake of off-site screening among those who refuse the self-sampling in arm 3 will be lower than uptake of off-site screening in arm 2

Objective 5: Examine the impact of HPV self-sampling on follow-up testing and care

Hypothesis 5.1: Women whose on-site HPV testing came out positive will go for follow-up testing and care

Objective 6: Assess the **feasibility** of the information session and the self-sampling test

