6.1. Quantitative data

The primary endpoint is the participation in screening which is defined in Arm 1 as the proportion of women who had a PAP smear taken by a GP or gynaecologist within the national screening program, in Arm 2 as the proportion of women who go for PAP smear after attending the information session with targeted referrals for off-site screening and in Arm 3 as the proportion of women who accept to take an HPV self-test on site after the information session.

Two important measures of take-up will be estimated:

Take-up 1 - To compare the take-up of an on-site HPV screening intervention with the current national screening services accounting for self-selection of women who decide to attend clinics (arm 1 vs. arm 3).

Take-up 2 - To compare the take-up of an on-site HPV screening intervention with targeted referrals to off-site screening (population impact regardless of self-selection) (arm 2 vs. arm 3).

Sample calculation was defined according to an estimated increase in take-up compared with current screening coverage for each study country.

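### Hypotheses 4.1 and 4.3 predict higher screening coverage than arm 1, but section 6.1 measures arms 2 and 3 as new tests after a session, which is not coverage

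*Protocol*

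**What the plan says.** **Hypotheses (protocol section 3.2).** Objective 4 is to "Compare the uptake of the on-site HPV testing (arm3) with the current national screening services (arm1) and with off-site referrals (arm2"). Under it, Hypothesis 4.1 (arm 3 against arm 1) reads "Uptake of on-site HPV self-sampling will result in an increase in screening coverage compared to standard practices". Hypothesis 4.3 (arm 2 against arm 1) reads "Referral to off-site screening following participation in an educational session on cervical cancer will result in higher screening coverage compared to current practices". Both are claims about coverage.

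**Endpoint (section 6.1).** Participation in screening is taken "in Arm 1 as the proportion of women who had a PAP smear taken by a GP or gynaecologist within the national screening program", with no look-back period. In arm 2 it is the share of women who go for a smear once they have attended the session; sections 3.1 and 4.6 place the check at a 3-month call. In arm 3 it is the share who accept the self-test at the session. The sample size sentence in 6.1 sets the expected increase in take-up against existing coverage in each country.

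**Arm 1 measures (sections 3.1 and 5.1).** Coverage is to be collected both nationally and for the local or hard-to-reach population.

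**Participants.** Section 4.2.1 has no criterion on screening history. Section 5.2.2.1 asks all participants whether they were screened in the last 3 years. Hypothesis 2.1 expects their uptake to be "lower than the national average (but similar to results found in arm 1").

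**Coverage figures (section 2).** "In Portugal and Belgium, screening coverages reaches 70.7% and 55%, respectively". Ecuador is given as 9 to 20% and Brazil as below 70%.

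**The concern.** Coverage is a stock: the share of women who are up to date, whenever they were tested. The arm 2 and arm 3 endpoints are flows: tests done within 3 months of a session, or at the session itself. A woman screened last year counts towards coverage, but she does not count in arm 2 unless she has another smear. No section of the protocol adds prior screening to new tests, or limits the endpoint to women who are overdue.

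Two of the four hypotheses under Objective 4 depend on this contrast. As written, a session that raises coverage substantially could be reported as leaving it below standard practice. The sample size sentence uses the same mixed scale. The protocol does not show the calculation, so its effect on the sample size cannot be judged.

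**Working it through.** The protocol gives no effect size, power or sample size to reproduce. The check is algebra, with illustrative inputs.

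**Notation**
- c: share of participants up to date at baseline (not given in the protocol).
- c1: arm 1 coverage. Hypothesis 2.1 expects c close to c1.
- eo, eu: shares of overdue and of up-to-date participants who are tested in the study (assumed).

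**Formulas**
- Endpoint under 6.1: E = c·eu + (1 − c)·eo.
- Rise in participants' coverage: G = (1 − c)·eo.
- Contrast with arm 1: D = E − c1, so D − G = c·eu − c1.
- If c1 = c, then D − G = −c(1 − eu), which is never positive. The contrast understates the rise, most of all when few up-to-date women are retested, as is plausible in arm 2.

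**Hypothesis 4.3 (arm 2), with eu = 0, eo = 40% and c1 = c**

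| c | Ceiling 1 − c | E | D (points) | Coverage after, c + G |
|---|---|---|---|---|
| 10% | 90.0% | 36.0% | +26.0 | 46.0% |
| 20% (Ecuador, upper figure) | 80.0% | 32.0% | +12.0 | 52.0% |
| 30% | 70.0% | 28.0% | −2.0 | 58.0% |
| 55% (Belgium, national) | 45.0% | 18.0% | −37.0 | 73.0% |
| 70.7% (Portugal, national) | 29.3% | 11.7% | −59.0 | 82.4% |

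D is negative whenever eo < c/(1 − c): below 11.1% at c = 10%, 25.0% at 20% and 42.9% at 30%. At 55% and 70.7% the ratio exceeds 1, so D is negative even if every overdue participant is screened.

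**Choice of arm 1 measure.** Take Belgium with c = 30% among participants and eo = 40%. Against a local figure of 30% the contrast is 28.0 − 30.0 = −2.0 points. Against the national 55% it is 28.0 − 55.0 = −27.0. The rise in coverage is 28.0 points in both cases.

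**Hypothesis 4.1 (arm 3), with the same acceptance in both groups and c1 = c = national figure**
- Belgium, 80%: D = 80.0 − 55.0 = +25.0; G = 0.45 × 0.80 = 36.0 points.
- Portugal, 80%: D = +9.3; G = 0.293 × 0.80 = 23.4 points.
- Portugal, 60%: D = −10.7; G = 0.293 × 0.60 = 17.6 points.

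Since G = E − c·eu ≥ E − c, a positive D implies a rise of at least D whenever c ≤ c1. Smears among women who decline the self-test are left out here; in overdue women they would only add to the rise.

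**The case against.** **Participants may all be overdue.** Sections 1 and 2 describe the target as women who are not, or not regularly, screened, and 6.1 does not say that up-to-date women are counted. Their inclusion is an inference from the eligibility list, the baseline questionnaire and Hypothesis 2.1, and their share is unknown. This limits what can be said about size. It does not remove the mismatch: with c = 0, new tests would still be set against a coverage figure from a population that includes screened women.

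**Self-selection and denominators.** Section 6.1 says that the comparison of arm 3 with arm 1 accounts for self-selection, and that the comparison with arm 2 disregards it, which might point to invited women as the denominator. How this is done can be left to an analysis plan. Neither choice turns new tests into coverage.

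**Limited consequence.** Arm 2 against arm 1 is not one of the two take-up measures that 6.1 singles out, and for Hypothesis 4.1 the error is mainly conservative. Both points stand.

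**Stronger readings that the protocol does not support**
- A reader might infer that the arm 3 versus arm 2 comparison is also compromised. Hypothesis 4.2 reads "On-site HPV self-sampling will have higher uptake than referrals to off-site screening", which is what 6.1 measures, and section 4.1 allocates organisations at random, so up-to-date status should not differ systematically by arm.
- A reader might infer that national coverage is the only comparator. The reference to national services can mean the type of service, and local coverage is also collected. This is a wording ambiguity to clear up.
- A reader might take the large Belgian and Portuguese gaps as expected results. They rest on national figures and assumed uptake, and Hypothesis 2.1 expects participants to be lower.

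**Conclusion.** The point holds for Hypotheses 4.1 and 4.3. The hypotheses are about coverage, the arm 2 and arm 3 endpoints count new tests, and the protocol itself fixes both.

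Hypothesis 4.3 is the more exposed. With no retesting of up-to-date women, it cannot be met where c exceeds 50%, and it can fail at lower c despite a real rise: in the illustration, −2.0 points at c = 30% against a rise of 28.0. At low c, such as Ecuador's 9 to 20%, the sign is more often right but the size is still understated. For Hypothesis 4.1 the main risk is a falsely negative or understated result. A positive difference would not be spurious, provided participants' baseline coverage is no higher than arm 1.

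The mismatch needs no assumption. The sizes rest on assumed values of eo and eu and on the value taken for c. This should be fixed before analysis; it does not undermine the randomised comparison of arm 3 with arm 2.

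**What to change.** 1. In 6.1, for Hypotheses 4.1 and 4.3, define coverage in arms 2 and 3 as screened in the last 3 years at baseline (first questionnaire) or newly screened in the study. Compare it with the participants' own baseline coverage and with arm 1 local or hard-to-reach coverage over the same stated look-back. Also report uptake among women not screened in the last 3 years, and label contrasts with arm 1 descriptive. Alternatively, reword both hypotheses as uptake hypotheses.
2. In Objective 4 and 6.1, state whether local/hard-to-reach or national coverage is the arm 1 comparator.
3. Keep the Hypothesis 4.2 comparison as planned.
4. Separately, reconcile the follow-up sections. Section 4.6 verifies Pap smears only in arm 2 and in HPV-positive arm 3 women. Hypothesis 4.4 concerns "Uptake of off-site screening among those who refuse the self-sampling in arm 3", and the arm 3 outcomes in 3.1 and the follow-up questionnaire in 5.2.2.4 carry no such restriction. The 3-month call should also record Pap smear status for arm 3 women who decline the self-sample.

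**Cost.** Low: the 3-year question and the call to all participants are already planned. The downsides are that prior screening is self-reported, local coverage may be unavailable in some countries, and the not-recently-screened group is smaller. If a share c is up to date, confidence intervals in that group widen by about 1/√(1 − c): 1.05, 1.20 and 1.41 times for c = 10%, 30% and 50%.

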A community-based researcher will educate women about sexual health and cervical cancer by using the materials that will be developed by the ELEVATE team. In addition, women will receive information about self-sampling and will be instructed by the community-based researcher on how to take a self-sample using an illustrative cartoon. Women will then be asked to take a sample on-site. The researcher will collect all samples and bring them to the laboratory of UZ Ghent for analysis by an HPV test (yet to be decided which one). Sample analysis is expected to take 2 weeks time. Women who tested positive for HPV will receive a follow-up phone call to notify their result and will again be informed about cervical cancer screening (pap smear) and about where they can obtain these services; they will receive a contact number to make an appointment as well as information on how to reach the place of the consultation.

Outcome measures that will be examined for arm 3 are:

- Participation rate (i.e., women invited/women who attend the session)
- Knowledge, willingness and uptake of cervical cancer screening prior to the session
- Acceptability of self-sampling
- Uptake of the self-sampling test (women who attend the session/women who take the self-sample)
- Attitudes towards self-sampling (reasons to accept/decline the self-sample; advantages and disadvantages versus conventional screening)
- User experiences among those who took a self-sample (easy/difficult; painless/painful; trustworthy/untrustworthy; etc.)
- Uptake of cervical cancer screening through standard services:
 - A 3-month follow up is proposed to check whether the woman made/went to the appointment
- Knowledge of as well as willingness to get screened for cervical cancer screening will also be assessed during the 3 month follow-up phone call
- Feasibility and cost of the intervention

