4.4. Educational sessions (arm 2 & 3)

Participants included will attend an information session. The information session will take place in the space where the group activities take place (provided by the organizations), the classroom of the integration course or a private room nearby the social restaurants. Sessions will be organized following the group activities (e.g. after sport activity, integration course or meal in social restaurant), with an approximate duration of 20 minutes (excluding sample taking). The sessions will be organized both during weekdays and weekends, depending on the activities they are linked to and according to the preferences of the organizations and women. The content of the session will cover sexual health, cervical cancer and screening services off-site. In the last part of the information session, participants in:

- **arm 2** - will be provided information on how to be screened for cervical cancer and where they can obtain these services off-site.
- **arm 3** - will be provided information on how to be screened for cervical cancer, and where they can obtain these services off-site. In addition, they will receive information on self-sampling and will be offered a self-sampling kit and asked to take a sample on-site and return it.

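### The primary endpoint counts an off-site smear as screening in arm 2 but not in arm 3, so Take-up 2 understates the arm 3 minus arm 2 difference in total screening among session attendees

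*Protocol*

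**What the plan says.** Section 6.1 opens with a single label: "The primary endpoint is the participation in screening". It then defines that endpoint separately for each arm:

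- Arm 2: "in Arm 2 as the proportion of women who go for PAP smear after attending the information session with targeted referrals for off-site screening".
- Arm 3: "in Arm 3 as the proportion of women who accept to take an HPV self-test on site after the information session".

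Take-up 2, the comparison of arms 2 and 3, is described in the same section as "population impact regardless of self-selection".

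Section 4.4 says that arm 2 attendees "will be provided information on how to be screened for cervical cancer and where they can obtain these services off-site". It says the same of arm 3 attendees and then adds the self-sampling information and kit. Section 3.1 lists "Uptake of cervical cancer screening through standard services" as an outcome in arm 3 as well as in arm 2. Hypothesis 4.4 in section 3.2 reads: "Uptake of off-site screening among those who refuse the self-sampling in arm 3 will be lower than uptake of off-site screening in arm 2". Nothing in section 6.1 brings these arm 3 smears into the primary endpoint.

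Two sections disagree on whether the smears are recorded. Section 4.6 directs the 3-month smear check at every arm 2 woman but, in arm 3, only at those who tested HPV-positive. Section 5.2.2.4 applies the follow-up questionnaire, including screening uptake, to both arms without that restriction.

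**The concern.** Organisations are randomised between arms 2 and 3 (section 4.1), so this is the protocol's randomised comparison. Its endpoint scores the same behaviour differently by arm. An attendee who goes for a smear after the session is a success if her organisation drew arm 2. If it drew arm 3 and she declined the brush, she is a failure.

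The label of the endpoint and the description of Take-up 2 both suggest that the comparison shows how many more women are screened under one strategy than the other. As defined, it cannot show that. It compares smears in arm 2 with self-tests in arm 3 and drops the smears of arm 3 decliners. The shortfall grows as acceptance of the self-test falls, which is also where the advantage of arm 3 would be least clear.

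**Working it through.** **Inputs.** The protocol gives no expected self-test acceptance, no expected smear uptake and no sample size, so there is no figure to reproduce. All rates below are assumptions.

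- a: self-test acceptance among arm 3 attendees
- d: smear uptake among arm 3 attendees who declined the self-test
- p2: smear uptake among arm 2 attendees

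**Formula.** Any screening in arm 3 = a + (1−a)d. The endpoint as defined gives a. Arm 2 is offered no self-test, so any screening in arm 2 is p2 under either definition. The arm 3 minus arm 2 difference is therefore understated by exactly (1−a)d.

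**Size of the undercount.**

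| a (endpoint as defined) | d = 10% | d = 30% | Any screening, arm 3 |
|---|---|---|---|
| 80% | 0.20 × 0.10 = 2 points | 0.20 × 0.30 = 6 points | 82–86% |
| 60% | 0.40 × 0.10 = 4 points | 0.40 × 0.30 = 12 points | 64–72% |
| 40% | 0.60 × 0.10 = 6 points | 0.60 × 0.30 = 18 points | 46–58% |

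**Can the sign change?** Only when acceptance is below p2. With p2 = 40%, a = 35% and d = 20% (d below p2, as Hypothesis 4.4 expects), the difference as defined is 35 − 40 = −5 points. Any screening in arm 3 is 0.35 + 0.65 × 0.20 = 48%, a difference of +8 points. With p2 = 20%, a = 70% and d = 10%, the difference only moves from 50 to 53 points.

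**Would the smears be recorded?** Under section 4.6, a decliner has no HPV result and so is not asked about a smear. Then neither d nor Hypothesis 4.4 can be estimated. Under section 5.2.2.4 she is asked. The corrected endpoint can be computed only if section 4.6 is brought into line.

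**Denominator.** Both arms' proportions in section 6.1 are taken after the session, so among attendees. Hypothesis 1.1 expects attendance to be higher in arm 3. Take p2 = 20%, a = 70% and, for simplicity, d = 0. The difference among attendees is 50 points whatever the attendance. Among invited women, with 50% attendance in arm 2:

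- arm 3 attendance 50%: 0.50 × 0.70 − 0.50 × 0.20 = 25 points
- arm 3 attendance 70%: 0.70 × 0.70 − 0.50 × 0.20 = 39 points

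So even with any screening as the endpoint, an attendee-based comparison is not a population effect.

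**The case against.** The best defence is that the definition fits the stated question. Objective 4 and Hypothesis 4.2 compare uptake of on-site self-sampling with uptake after off-site referral, and a comparison of one mode with the other is a legitimate estimand. The reference to self-selection in Take-up 2 may only be there to contrast it with Take-up 1. Arm 3 smears are not forgotten either: they are a listed outcome, and Hypothesis 4.4 concerns them. The statistical analysis plan, not shown here, might add an any-screening analysis.

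Much of this stands. Self-test uptake does answer Hypothesis 4.2 literally and should be kept. What remains is the mismatch between that definition and the endpoint's own label and stated purpose, and section 6.1 fixes both.

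A reader might infer more than the documents support:

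- **That arm 3 receives the whole arm 2 package plus the self-test.** Section 3.1 gives all arm 2 women a contact number and directions, but mentions these in arm 3 only for HPV-positive women. Section 6.1 uses the term targeted referrals for arm 2 alone. The off-site information shared under section 4.4 is enough for this point; an identical referral is not established.
- **That the endpoint favours self-sampling.** The omission can only lower arm 3. It works against Hypothesis 4.2 and cannot produce a false benefit.
- **That 18 points is an estimate.** It needs both 40% acceptance and 30% smear uptake among decliners, and the protocol supplies neither.
- **That counting the smears would turn Take-up 2 into a population effect.** The attendee denominator prevents that.

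**Conclusion.** The point holds as a mismatch between what the primary endpoint is called and what it counts. Among session attendees, the arm 3 minus arm 2 difference in total screening is understated by (1−a)d, within the assumed ranges tabulated above. If most women accept the self-test, the effect is small. It matters for the size of the effect and, only when acceptance is below arm 2 smear uptake, for its direction. It does not undermine a positive result for self-sampling. The matter is worth correcting because it concerns the primary endpoint of the randomised comparison, and because section 4.6 as written would leave the missing smears unrecorded.

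**What to change.** Three changes:

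1. **Section 6.1.** Define the Take-up 2 endpoint identically in both arms: any cervical screening, by self-sample or Pap smear, from the session to the 3-month call. Count each woman once. Report on-site self-sample uptake beside it as the literal answer to Hypothesis 4.2.
2. **Section 4.6.** Remove the restriction to HPV-positive women in arm 3, so that all arm 3 women, including decliners, are asked about a smear. This agrees with section 5.2.2.4 and makes Hypothesis 4.4 measurable. Smears after a positive self-test remain the data for Objective 5.
3. **Section 6.1, description of Take-up 2.** Call it an effect among session attendees, since the denominator is attendees and Hypothesis 1.1 expects attendance to differ by arm.

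The cost is a few sentences and one question in a call already planned for all participants. The downside is that the arm 3 endpoint is complete only at 3 months instead of on the day. Its off-site part would also rest on self-report and be subject to loss to follow-up, as the arm 2 endpoint already is. Women not reached should be handled the same way in both arms.

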3.1. Study design

A 3-arm prospective acceptability study will be conducted with the following study arms:

Arm 1 – Assessment of screening coverage

Information about the screening coverage rates will be collected, focusing in particular on screening uptake among hard-to-reach women. The screening rates will be collected prior to the start of the study to avoid any contamination, i.e. uptake of screening that may occur through community mobilisation.

Outcome measures that will be examined for arm 1 are:

- Screening coverage at national level
- Screening coverage at local level/in hard-to-reach communities
- Follow-up rate among women who test positive (i.e., have a positive pap smear)

Arm 2 – Information session and follow-up assessment

In arm 2, a community-based researcher will educate women about sexual health and cervical cancer by using the materials that will be developed by the ELEVATE team. Women will be informed about cervical cancer screening (pap smear) and about where they can obtain these services off-site (health facilities); they will receive a contact number to make an appointment as well as information on how to reach the place of the consultation.

Outcome measures that will be examined for arm 2 are:

- Participation rate (i.e., women invited/women who attend the session)
- Knowledge, willingness and uptake of cervical cancer screening prior to the session
- Acceptability of self-sampling
- Uptake of cervical cancer screening through standard services: A 3-month follow-up by phone is proposed to check:

- whether the woman made an appointment; if no appointment was made, we will ask why; if an appointment was made, we will ask if she was able to attend the appointment
- Knowledge of as well as willingness to get screened for cervical cancer screening will also be assessed during the follow-up phone call
- Feasibility

Arm 3 – Information session and self-sampling

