5.1. Arm1

We will contact the respective instances in each study country to ask if more detailed data are available on screening coverage of the target group of socio-economically vulnerable women.

Outcome measures that will be examined for arm 1 are:

- Screening coverage at national level
- Screening coverage in the respective research area in each study country
- Follow-up rate among women who test positive (i.e. have a positive pap smear)

5.2. Arm 2 and arm 3

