6.2. Qualitative data

Audio recordings of the interviews will be transcribed, and the transcripts will be analysed through content analysis. This technique allows the data to be systematized in key topics and organized in different categories and sub-categories. Simultaneously, written notes taken during the interviews will be also used to improve and complete the information if considered relevant.

7. Data management

All data will be entered in a Redcap. In total, the following information will be entered:

- 1) Participation registers
- 2) Self-administered questionnaire among all (KAP)
- 3) 2 self-administered questionnaire in arm 3 (attitudes towards (=pre-intervention) and users' experience (=post-intervention))
- 4) Telephone questionnaire (=follow-up assessment)

The unique identifier code will be used to link all the questionnaires of the same participant and to ensure pseudonymization of the data.

Only members of the research team will have access to the pseudonymized data: the data will be saved on work computers of team members only, and a back-up will be saved on a protected server that can only be accessed with a username and password.

8. Training community-based researchers

Both researchers with a medical background and community-based researchers will be involved in all stages of the study. Researchers with a medical background and medical students (in the broad sense, including students studying medicine, health promotion, biomedical sciences, etc.) will assist during the educational sessions and possibly, after they followed some sessions provided by the main researcher (gynecologist), give the sessions themselves. Community-based researchers including social workers and community (health) workers will equally be involved in all stages of this study; however, their core responsibilities will be participant recruitment, assisting during the educational sessions, assisting during self-sampling and (post) counselling, and data collection (questionnaires).

Both groups of researchers will be provided training. The training will cover: HPV and cervical cancer, screening and diagnosis of cervical cancer, follow up of cervical lesion; research methods for the project and their specific tasks; interpersonal communication skills; appropriate responses to sensitive

information (i.e. how to react to women who share experiences of sexual violence, stigma, ill health, etc.); appropriate communication of results.

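### Take-up 1 is said to account for self-selection, but the arm 1 data as described cannot support that adjustment

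*Protocol*

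**What the plan says.** Section 6.1 of the Protocol names two take-up measures. Take-up 1 sets on-site HPV screening against existing services: "with the current national screening services accounting for self-selection of women who decide to attend clinics (arm 1 vs. arm 3"). Take-up 2 is arm 2 against arm 3 and is labelled a population impact that disregards self-selection. For the existing services the endpoint reads "defined in Arm 1 as the proportion of women who had a PAP smear taken by a GP or gynaecologist within the national screening program"; for the self-sampling arm it reads "in Arm 3 as the proportion of women who accept to take an HPV self-test on site after the information session".

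Other sections describe what arm 1 consists of:

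- Section 3.1: "The screening rates will be collected prior to the start of the study to avoid any contamination".
- Section 5.1: the responsible bodies in each country will be contacted "to ask if more detailed data are available on screening coverage of the target group of socio-economically vulnerable women". The listed outcomes are national coverage, "Screening coverage in the respective research area in each study country", and the follow-up rate after a positive smear.
- Section 4.1: organisations are randomised between arms 2 and 3 only.
- Section 7 opens its list of data with "In total, the following information will be entered". The items are the registers and questionnaires that section 5.2 describes for arms 2 and 3. None belongs to arm 1.

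**The concern.** Section 6.1 gives one of its two take-up measures a specific property, an allowance for self-selection into clinics. That needs information on who attends clinics and who does not, in a form that can be related to the arm 3 women. The protocol describes no such information for arm 1.

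Arm 3 adds selection of its own. Its women accepted an invitation that mentions the self-test (section 4.3) and stayed for the session. The inclusion criteria in section 4.2.1 do not require a woman to be unscreened or overdue. A self-sample from a recently screened woman therefore counts as take-up, although it does not add to coverage in the sense of Hypothesis 4.1.

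At stake is what may be concluded for Hypothesis 4.1. Section 6.1 also bases the sample size on an increase over current coverage, which is a contrast with this same benchmark. If the clause stands, a difference from historical coverage could be read as already corrected for selection.

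**Working it through.** The protocol states no sample size, power or effect size, so there is no figure to reproduce. The check sets the sections against each other and then gauges how much the contrast could move.

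**1. What the adjustment would need.** Arm 1 is described as rates, dated before the study, not randomised, and absent from the list in section 7. On the arm 3 side, section 5.2.1 counts women who do not attend only through the number of leaflets handed out. Section 5.2.2 records participants' screening history and barriers, but only for women who came. Choice of model cannot supply the missing arm 1 information.

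**2. Attendees or invited women.** Let c be coverage (section 2), s acceptance among attendees and a attendance among invited women; s and a are assumed. Take-up per invited woman is a × s, which exceeds c only if a > c / s.

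| Country | c | s − c at s = 80% | c / s at s = 90% | c / s at s = 80% |
|---|---|---|---|---|
| Belgium | 55% | +25 points | 0.55/0.90 = 61% | 0.55/0.80 = 69% |
| Portugal | 70.7% | +9.3 points | 0.707/0.90 = 79% | 0.707/0.80 = 88% |
| Brazil | below 70% | at least +10 points | at most 0.70/0.90 = 78% | at most 0.70/0.80 = 87.5% |
| Ecuador | 9% to 20% | +71 to +60 points | 10% to 22% | 11% to 25% |

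At s = 90% and a = 50%, take-up per invited woman is 0.50 × 0.90 = 45%, below Belgium and Portugal, while the figure among attendees (90%) is above all four countries. At s = 60%, Belgium's threshold is 0.55/0.60 = 92%; Portugal, and Brazil if its coverage is at the 70% limit, are then below coverage even at full attendance. Each threshold is proportional to c, so a lower local or hard-to-reach benchmark lowers it in proportion.

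This step changes the denominator. It is not itself a model of selection, so a separate check follows.

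**3. Selection into the session.** Let p be the share of the target group who would take up the test, and suppose willing women attend r times as often as unwilling women (r assumed). Take-up among attendees is p × r / (p × r + 1 − p).

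- No true difference (p = c), r = 2. Belgium: 1.10 / (1.10 + 0.45) = 71% against 55%. Brazil at 70%: 1.40 / 1.70 = 82%. Portugal: 1.414 / 1.707 = 83% against 70.7%. Ecuador: 17% against 9%, or 33% against 20%.
- True deficit of 10 points (p = c − 0.10). It appears as a gain once r exceeds [c/(1 − c)] / [p/(1 − p)]: 1.49 in Belgium, 1.56 in Brazil (at 70%) and Portugal, and 2.25 in Ecuador at 20%.
- True gain of 10 points (p = c + 0.10), r = 0.5. It reads as −6.9 points in Belgium, −3.3 in Brazil, −3.1 in Portugal and −2.4 in Ecuador at 20%, but +1.5 in Ecuador at 9%.

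The error can run either way. Willing women may be more likely to come. On the other hand, arm 3 recruits hard-to-reach women, while the coverage figures in section 2 refer to the eligible population at large.

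**The case against.** The strongest reply is that the protocol leaves room for better data. Section 5.1 asks for more detail on the target group, section 3.1 lists coverage in hard-to-reach communities, and stratified rates would allow standardisation on measured factors. Section 5.2.2 records each participant's lifetime and recent screening and her reasons for or against a smear. Hypothesis 2.1 compares participants' previous uptake with arm 1, which is a partial check of comparability. How these data are used may be left to an analysis plan that is not shown.

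Much of this stands. A reader might infer that arm 1 has no individual data or covariates at all, or that no adjustment is possible. The documents do not say so: more detail is uncertain, not excluded. Still, stratified rates would correct for measured factors such as age and area, not for the decision to attend a clinic, and arm 3 screening history says nothing about the women behind the arm 1 rates.

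A reader might also infer that selection alone will reverse the result. The figures show only that it could, at values of a, s and r that the protocol does not give and against general rather than hard-to-reach coverage.

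The clause might merely acknowledge that self-selection is present in the comparison. Next to the contrasting label on Take-up 2 it reads as an adjustment, so it needs rewording in either case.

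Visiting an organisation defines the target population and is no flaw. Section 3.1 introduces the arms with "A 3-arm prospective acceptability study will be conducted with the following study arms", but it says openly that the arm 1 rates predate the study, so that label is an editorial matter.

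**Conclusion.** The point holds as a mismatch between a stated property and the data described: section 6.1 claims an allowance for self-selection that the arm 1 data, as set out in sections 3.1, 5.1 and 7, cannot support. Since the limit lies in what is collected, an analysis plan could not remove it by choice of model alone.

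The size is conditional. A sign change is within reach for Belgium, Brazil and Portugal at moderate assumed values; in Ecuador it takes low attendance or stronger selection. None of this predicts the direction of the actual error. The conclusion rests on the wording of the protocol, and the figures only show that the matter is not negligible.

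**What to change.** In section 6.1:

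- Delete the self-selection clause from Take-up 1. Describe it as a descriptive comparison with a historical benchmark, using the local or hard-to-reach rate where one is obtained, with no causal claim for Hypothesis 4.1.
- Where the arm 1 source gives rates by age band or area, standardise them to the mix of the arm 3 women.
- Show arm 3 take-up by screening in the last 3 years, which the first questionnaire already asks.
- Base inference about an effect on Take-up 2, the only randomised contrast. Report it per invited woman as well, because Hypothesis 1.1 expects attendance to differ between the arms. The registers give the denominator, and arm 2 also needs the 3-month follow-up data. Since section 4.3 asks women to invite others, the leaflet count is an approximate denominator and should be labelled as such.

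Optionally, note in section 3.1 that arm 1 is not prospective.

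The cost is protocol wording, a simple standardisation and two extra tabulations, with no new data collection. The downside is a weaker claim for Hypothesis 4.1.
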